**Table 4 Randomized Controlled Period Schedule of Study Assessments for the MuSK-Ab+ Population**

Study Period	RCP						
Study Week	0	2	4	8	12	18	26
Study Day (visit window)	Day 1	Day 15 (±2d)	Day 29 (±3d)	Day 57 (±3d)	Day 85 (±3d)	Day 126 (±7d)	Day 183 a (±7d) or EDV b
Verify eligibility criteria	X						
MGQOL-15r score; PGIC; [REDACTED]	X		X	X	X	X	X
C-SSRS (Baseline/Screening version)	X						
C-SSRS (Since Last Visit version)		X	X	X	X	X	X
Weight	X						X
Height	X						
ECG	X	X					X
Vital signs	X	X	X	X	X	X	X
Concomitant medications	X	X	X	X	X	X	X
MG-ADL score c	X	X	X	X	X	X	X
QMG score c	X		X	X	X	X	X
MGC score c	X		X	X	X	X	X
MGFA clinical classification	X						X
Physical examination	X				X		X
Collect blood for: d							
Hematology and serum chemistry	X	X	X	X	X	X	X
Inebilizumab PK (serum) e	X	X	X	X	X		X
Inebilizumab ADA (serum)	X		X		X		X

**Table 4 Randomized Controlled Period Schedule of Study Assessments for the MuSK-Ab+ Population**

Study Period	RCP						
Study Week	0	2	4	8	12	18	26
Study Day (visit window)	Day 1	Day 15 (±2d)	Day 29 (±3d)	Day 57 (±3d)	Day 85 (±3d)	Day 126 (±7d)	Day 183 a (±7d) or EDV b
Urine pregnancy test g	X	X					
IP administration h	X	X					
Assessment of AEs/SAEs	X	X	X	X	X	X	X
Corticosteroid dispense i	X		X	X	X		
Telephone follow-up (Japan only)	In Japan only, telephone calls should be made every 2 weeks starting from Day 43 (Week 6) and continuing for the duration of the RCP, except for study visit weeks						

ADA = anti-drug antibody(ies); AE = adverse event; C-SSRS = Columbia-Suicide Severity Rating Scale; d = Day; ECG = electrocardiogram; EDV = Early Discontinuation Visit; [REDACTED]; IP = investigational product; MG-ADL = Myasthenia Gravis Activities of Daily Living; MGC = Myasthenia Gravis Composite; MGFA = Myasthenia Gravis Foundation of America; MGQOL-15r = Myasthenia Gravis Quality of Life-15, revised [REDACTED]; [REDACTED]; OLP = Open-label Period; PGIC = Patient global impression of change; [REDACTED]; PK = pharmacokinetic(s); QMG = Quantitative Myasthenia Gravis; RCP = Randomized Controlled Period; [REDACTED]; SAE = serious adverse event; SFU = safety follow-up.

- a. For subjects choosing to continue into the OLP, Day 183 visit procedures need to be completed prior to starting any procedures or doses of the first day of Open-label Extension. Subjects who decide not to participate in the OLP (but complete Day 183 visit), will be asked to enter the SFU Period (see [Section 6.1.4](#)).
  - b. An EDV should be performed for any MuSK-Ab+ subject who withdraws prior to the RCP Week 26 visit (see [Section 6.3.2](#)); subjects that discontinue the IP will be asked to remain in the study and complete all RCP study visits and assessments with the exception of those related to directly to dosing (see [Section 6.3.1](#)).
  - c. Assessment should be performed at approximately the same time of day for all visits and, if possible, completed by the same assessor. Acetylcholinesterase inhibitors (if taken) must be held for 6 hours prior to the assessments; see [Section 6.2.5.3](#) for additional information.
  - d. Fasting is not required.
  - e. On inebilizumab dosing days (Days 1 and 15), inebilizumab PK serum samples are to be collected predose and approximately 15 minutes ( $\pm$  5 minutes) after completion of the IP infusion. On non-dosing days, only one PK serum sample is required.
- 
- h. Females of childbearing potential only; must be found negative before the IP is administered.
  - i. On days of IP administration, all procedures and blood sampling, except for post dose PK, must be collected before IP administration.
  - j. For subjects on corticosteroids. Note: corticosteroid dispensation may occur outside of the scheduled visit timepoints if required/necessary to dispense the necessary quantity to subjects as needed. For corticosteroid tapering schedule, refer to [Table 12](#).

### 6.1.3 Open-label Period

Subjects who complete the RCP have the option to enroll in the OLP study. Subjects who discontinue the RCP early are not eligible to enter the OLP. Informed consent for OLP participation must be obtained at the time of OLP entry.

The study OLP duration is 3 years for both study populations, AChR+ and MuSK+. The OLP assessments are the same for both study populations.

Upon completing all the assessments at the last RCP visit, it is strongly recommended to perform the OLP Day 1 visit on the same day. The OLP Day 1 visit may occur for up to 14 days after the final RCP visit. Many assessments are common to both the final RCP visit and OLP Day 1 visit and do not need to be repeated if done within 14 days of the final RCP visit (see [Table 5](#), footnote b). Subjects are not permitted to enter the OLP after 14 days after the final RCP visit without the Sponsor's written approval.

During the OLP, subjects' treatment assignment will remain blinded. The OLP will include IP infusions on OLP Days 1, 15, and 183, and every 6 months thereafter at Days 365, 547, 729, and 911. All subjects will receive inebilizumab on OLP Days 1, 183, 365, 547, 729, and 911. On OLP Day 15, subjects who received inebilizumab in the RCP will receive placebo and subjects who received placebo in the RCP will receive inebilizumab. This will allow subjects who are just beginning inebilizumab to receive the full 2-dose initial treatment course while maintaining blinding of the RCP treatment assignment.

For more details about OLP assessments, see [Table 5](#).

Subjects will continue to be followed for an additional 26 weeks after the last dose of inebilizumab (at OLP Day 911) until OLP Day 1093.

It is recommended to taper non-steroidal ISTs (eg, azathioprine, mycophenolate mofetil, mycophenolic acid) per standard of care. For subjects on tacrolimus (allowed in Japan only), taper of tacrolimus is recommended. The rationale for tapering non-steroidal ISTs in the OLP is to reduce potential risks associated with long-term use of multiple ISTs.

Corticosteroids can either be continued at a dose of prednisone 5 mg daily or can be tapered at the discretion of the Investigator. If a subject receives a dose of prednisone that is > 10 mg daily for > 8 consecutive weeks in the OLP, then the IP must be discontinued ([Section 6.3.1](#)). The rationale for this requirement is to reduce the potential risk of adverse effects associated with long-term combination of moderate- or high-dose corticosteroids and inebilizumab.

**Table 5 Open-label Period Procedures for AChR-Ab+ and MuSK-Ab+ Populations**

Study Period	OLP										
OLP week	0	2	13	26	39	52	65	78	104	130	156
OLP Study Day (visit window)	Day 1 a	Day 15 (±2d)	Day 92 (±7d)	Day 183 (±7d)	Day 275 (±7d)	Day 365 (±7d)	Day 456 (±7d)	Day 547 (±7d)	Day 729 (±20d)	Day 911 (±20d)	Day 1093 (±20d) or EDV k
Written ICF	X b										
Verify eligibility criteria	X										
MGQOL-15r score; PGIC; [REDACTED]	X b		X	X	X	X	X	X	X	X	X
C-SSRS (Since Last Visit version)	X b	X	X	X	X	X	X	X	X	X	X
Weight	X b					X					X
Vital signs	X	X	X	X	X	X	X	X	X	X	X
Concomitant medications	X	X	X	X	X	X	X	X	X	X	X
MG-ADL score c	X b	X	X	X	X	X	X	X	X	X	X
QMG score c	X b		X	X	X	X	X	X	X	X	X
MGC score c	X b		X	X	X	X	X	X	X	X	X
MGFA clinical classification	X b			X		X		X	X	X	X
Physical examination	X b		X	X	X	X	X	X	X	X	X
Collect blood for: d											
Hematology and serum chemistry	X b	X	X	X	X	X	X	X	X	X	X
Inebilizumab ADA (serum)	X b		X	X	X	X		X	X	X	X

**Table 5 Open-label Period Procedures for AChR-Ab+ and MuSK-Ab+ Populations**

Study Period	OLP										
OLP week	0	2	13	26	39	52	65	78	104	130	156
OLP Study Day (visit window)	Day 1 a	Day 15 (±2d)	Day 92 (±7d)	Day 183 (±7d)	Day 275 (±7d)	Day 365 (±7d)	Day 456 (±7d)	Day 547 (±7d)	Day 729 (±20d)	Day 911 (±20d)	Day 1093 (±20d) or EDV k
Urine pregnancy test h	X	X		X		X		X	X	X	X
IP administration i	X	X		X		X		X	X	X	
Assessment of AEs/SAEs	X	X	X	X	X	X	X	X	X	X	X
Corticosteroid dispense j	X		X	X	X	X	X	X	X	X	

██████████; **ADA** = anti-drug antibody(ies); **AE** = adverse event; **C-SSRS** = Columbia-Suicide Severity Rating Scale; **d** = Day; **ECG** = electrocardiogram; **EDV** = Early Discontinuation Visit; **ICF** = informed consent form; ██████████; **IP** = investigational product; **MG-ADL** = Myasthenia Gravis Activities of Daily Living; **MGC** = Myasthenia Gravis Composite; **MGFA** = Myasthenia Gravis Foundation of America; **MGQOL-15r** = Myasthenia Gravis Quality of Life-15, revised ██████████ ██████████  
██████████; **OLP** = Open-label Period; **PGIC** = Patient Global Impression of Change; ██████████; **QMG** = Quantitative Myasthenia Gravis; ██████████; **SAE** = serious adverse event; **SFU** = safety follow-up.

- For subjects choosing to continue into the OLP, end of RCP visit procedures must be completed prior to starting any procedures or doses of the first day of OLP.
- This procedure does not need to be repeated on OLP Day 1 if it was completed at the final RCP visit and the OLP Day 1 visit is done within 14 days of the final RCP visit.

- c. Assessment should be performed at approximately the same time of day for all visits and, if possible, completed by the same assessor. Acetylcholinesterase inhibitors (if taken) must be held for 6 hours prior to the assessments; see [Section 6.2.5.3](#) for additional information.
  - d. Fasting is not required.
- 
- h. Females of childbearing potential only; must be found negative before the IP is administered.
  - i. On days of IP administration, all procedures and blood sampling must be collected before IP administration.
  - j. For subject on corticosteroids; corticosteroid dispensation may occur outside of the scheduled visit timepoints if required/necessary to dispense the necessary quantity to subjects as needed.
  - k. Subjects who discontinue the IP during the OLP should complete an EDV and be asked to participate in the SFU Period (see [Section 6.1.4](#)).

#### 6.1.4 Safety Follow-up

Following the last administration of IP (either the last scheduled dose of IP or the last administration prior to the IP discontinuation), all subjects will enter the SFUP. Safety Follow-Up Visits will occur for up to 2 years after the last administration of IP, or until recovery of peripheral CD20+ B cell counts and [REDACTED], whichever occurs first. During this time subjects will be seen every six months in-clinic for blood draws and other limited assessments.

Assessments and procedures during the SFU Period are detailed in [Table 6](#).

**Table 6 Safety Follow-up Period**

Study Period	Safety Follow-up
Safety Follow-up Weeks	Every 26 weeks from time subject completes treatment/discontinues IP (up to 2 years)
Visit Window	± 4 weeks
Assessment of AEs and SAEs	X
Assessment of concomitant medications	X
Hematology and serum chemistry	X
Blood collection for: [REDACTED]	X

AE = adverse event; [REDACTED]; IP = investigational product; SAE = serious adverse event.

#### 6.1.5 Special Visit Types (occurring during RCP and OLP)

##### 6.1.5.1 Remote Visits and/or Procedures

In exceptional circumstances and with prior agreement of the medical monitor, particular study visits or procedures may be performed remotely (via teleconference, video conference, or similar) if the subject is not able to physically attend the clinic for that visit or procedure (eg, due to COVID-19 restrictions). Missed assessments during remote visits, regardless of medical monitor agreement, will incur protocol deviations. Refer to [Table 7](#).

##### 6.1.5.2 Clinical Deterioration Visit

A Clinical Deterioration Visit should be performed if a subject complains of worsening MG symptoms and use of rescue therapy is being considered. This should be performed before the rescue therapy is initiated. The procedures to be performed are listed in [Table 7](#). Additional details on the use of rescue therapy can be found in [Section 7.2.2](#).

##### 6.1.5.3 Unscheduled Visit

An Unscheduled Visit is performed to address and complete scheduled trial-related activities that are not associated with Clinical Deterioration, such as to repeat hemolyzed blood samples or missing or incomplete assessments or as a follow-up for an AE, as needed. A potential list of the

assessments and procedures for unscheduled visits are listed in [Table 7](#) and should be performed at the discretion of the Investigator.

Visit Type	Remote Visit	Clinical Deterioration Visit	Unscheduled Visit h
Prior approval from Medical Monitor	X		
MGQOL-15r score; PGIC; ██████████	X	X	P
C-SSRS (Since Last Visit version)	X	X	P
ECG		P	P
Vital signs		X	P
Concomitant medications	X	X	P
MG-ADL score a	X	X	P
QMG score a		X	P
MGC score a		X	P
MGFA clinical classification		X	P
Physical examination		P	P
Collect blood for b:			
Hematology and serum chemistry		P	P
Inebilizumab PK (serum) c		X	P
Inebilizumab ADA (serum)		X	P
IP administration			
Assessment of AEs/SAEs	X	X	X
Corticosteroid dispense g			P

P = potential procedure/assessment to be performed at the discretion of the Investigator and with participant's agreement; **PGIC** = Patient Global Impression of Change; [REDACTED]; **PK** = pharmacokinetic(s); **QMG** = Quantitative Myasthenia Gravis; **RCP** = Randomized controlled period; [REDACTED]; **SAE** = serious adverse event.

- Page 54 of 130

- b. Fasting is not required.
- c. Inebilizumab PK (serum) is only collected during RCP; if special visit occurs during OLP, sample is not obtained.

- f. Females of childbearing potential only; must be found negative before IP is administered.
- g. For subject on corticosteroids; note: corticosteroid dispensation may occur outside of the scheduled visit timepoints if required/necessary to dispense the necessary quantity to subjects as needed.
- h. If an Unscheduled Visit is performed, the Investigator should select the relevant subset of assessments to perform.

## 6.2 Description of Study Procedures

### 6.2.1 Informed Consent

All candidates for enrollment will sign an ICF prior to any protocol-related procedures, including screening activities. Informed consent must be obtained by the Investigator or a designee, such as an Investigator with Institutional Review Board (IRB)/Independent Ethics Committee (IEC) approved qualifications. See [Section 10.3](#) for additional details.

Subjects who are  $\geq 18$  years of age but under the age of consent in their respective country must sign their assent, and their legally authorized representative must sign consent prior to any protocol-required procedures. If they reach the age of consent while on the study, they will be asked to sign an ICF in order to document their consent to be on the study.

In addition to the main study participation, subjects will be asked if they consent to 2 optional aspects (if applicable in that country): 1) use of leftover blood samples for future research, and 2) [REDACTED], efficacy, PK, and [REDACTED]. Additional details of the genetic analysis are found in [Section 6.2.8.8](#).

After signing the ICF, each subject will be assigned a subject identification (SID) number that will be used on all subject documentation. Numbers will be assigned in ascending sequential order. This number will also correspond to the subject number entered on test materials. Re-screened subjects will receive a new SID number.

As noted in [Section 6.1.3](#), in addition to the ICF signed for the RCP period, written informed consent for OLP participation must be obtained at the time of OLP entry.

### 6.2.2 Demographics, Medical, and Disease History

Demographic information to be collected includes year of birth, sex, race, and ethnicity. Medical history information to be collected includes all ongoing conditions and relevant/significant medical history (including all major hospitalizations and surgeries), as determined by the Investigator. Concomitant medications will be recorded. MG medication history will be recorded, including use of 1) chronic MG immunosuppressive medications and 2) use of rescue therapy in the prior 2 years.

### 6.2.3 Confirmation of Myasthenia Gravis Antibody Status

For subjects with a prior positive result for antibodies to AChR or MuSK, that specific antibody will be tested in the screening labs to confirm positivity. If antibody testing was not previously

done or the results of prior antibody testing are not known, the subject can still be screened and both AChR and MuSK antibodies should be tested during screening. If a subject is not confirmed to be positive for anti-AChR or anti-MuSK antibodies by the central laboratory, then the subject cannot be randomized and must fail the screen. If a site desires a retest due to an unexpected negative result, an Unscheduled Visit can be performed, and a new blood sample can be submitted for testing. If necessary, the screening period can be extended up to 28 days to accommodate the retest if approved by the medical monitor. If a subject is positive for both anti-AChR and anti-MuSK antibodies, the subject should be enrolled in the MuSK-Ab+ group.

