## 5 POPULATION

### 5.1 Inclusion Criteria

To be included in this study, each individual must satisfy all the following criteria:

1. Male or female subjects  $\geq 18$  years old.
2. Written informed consent and any locally required authorization (eg, Health Insurance Portability and Accountability Act in the United States of America, European Union Data Privacy Directive in the EU) obtained from the subject prior to performing any protocol-related procedures, including screening evaluations. In countries where the legal adult age is  $> 18$  years, subjects  $\geq 18$  years but under legal age for that country must also provide assent and have consent of a parent or other legally authorized representative.
3. Diagnosis of MG defined as:
  - a. Positive serologic test for anti-AChR or anti-MuSK antibody titers as confirmed at screening (one retest allowed), and
  - b. At least one of the following:
    - History of abnormal neuromuscular transmission test results demonstrated by single-fiber electromyography or repetitive nerve stimulation; or
    - History of positive anticholinesterase test (eg, edrophonium chloride test); or
    - Subject demonstrated improvement in MG signs on oral acetylcholinesterase inhibitors, as assessed by the treating physician; or
    - Clinical syndrome consistent with a diagnosis of MG and not otherwise explained by another condition.
4. MGFA Clinical Classification Class II, III, or IV at the time of screening and randomization.
5. MG-ADL score at the time of screening and randomization between 6 and 10 with  $> 50\%$  of this score attributed to non-ocular items or an MG-ADL score  $\geq 11$ .
6. QMG score of  $\geq 11$  or greater at the time of screening and randomization.
7. Subjects must be on:
  - a. Corticosteroids only, with no dose increase within 4 weeks prior to randomization, or
  - b. One allowed non-steroidal IST, with continuous use for  $\geq 6$  months prior to randomization and no dose increase within 4 months prior to randomization, or
  - c. Combination of 1) corticosteroids with no dose increase within 4 weeks prior to randomization and 2) one allowed non-steroidal IST with continuous use for  $\geq 6$  months prior to randomization and no dose increase within 4 months prior to randomization.

Allowed ISTs, alone or in combination with corticosteroids, are azathioprine, mycophenolate mofetil, and mycophenolic acid.

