**Table 2 Screening Procedures (Visit 1)**

Study Period	Screening
Visit Number	V1
Procedure/Study Day	Day -28 to Day -1
Written informed consent	X
Review eligibility criteria	X
Medical and disease history	X
Demographics	X
Weight	X
ECG	X
Vital signs	X
Concomitant medications	X
MG-ADL score	X
QMG score a	X
Collect blood for b:	
Hematology and chemistry	X
Serum $\beta$ -hCG (females of childbearing potential only)	X
FSH (postmenopausal female subjects only)	X
Hepatitis B, C; HIV	X
	X
Serum for AChR or MuSK serostatus c	X
	X

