### 6.1.2 Randomized Controlled Period

The duration of the RCP will be 52 weeks for the AChR-Ab+ population and 26 weeks for the MuSK-Ab+ population. The primary efficacy endpoint will be measured at 26 weeks for both study populations.

Based on the previous study experience with inebilizumab in NMOSD, CD19-mediated B-cell depletion was efficacious within 26 weeks. Similar efficacy is anticipated in AChR-Ab+ and MuSK-Ab+ MG within 26 weeks, supported by clinical experience using B-cell-depleting agents in generalized MG.

All study assessments until Week 26 are common for both study populations.

The schedule of study assessments during the RCP is presented in [Table 3](#) for the AChR-Ab+ population and in [Table 4](#) for the MuSK-Ab+ population.

After 26 weeks of the RCP, MuSK-Ab+ subjects may progress to the OLP. AChR-Ab+ subjects will continue the RCP for a total of 52 weeks in a blinded fashion. To ensure the blinding of each subject's treatment assignment during the study, the study site personnel, the Sponsor personnel who are directly associated with the conduct of the study, and the subjects will remain blinded to the treatment assignment until completion of the RCP. Completion of the full 52 weeks of the RCP will provide additional safety data collected in an unbiased, double-blind manner.

The full RCP schedule of assessments is different for AChR-Ab+ and MuSK-Ab+ subjects.

All procedures must be completed prior to administration of the IP except for collection of AEs, specific postdose blood samples, and corticosteroid dispensing.

In Japan only, it is required for the site to call subjects every 2 weeks during the RCP beginning at Day 43 (Week 6). The purpose of the telephone call is to assess the clinical status of the subject. It is not necessary to call subjects during a week when a study visit will occur.

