#### **7.3.2 Randomization Strategy and Procedure**

An interactive voice/web response system (IXRS) will be used for randomization to a treatment group and assignment of IP kit numbers. Subjects will be enrolled into either the AChR-Ab+ or MuSK-Ab+ population. Within each population, subjects will be stratified by region first (non-Japan vs Japan). In the non-Japan population, subjects will be further stratified according to baseline disease severity ("Day 1 QMG score = 11-15" vs "Day 1 QMG score  $\geq 16$ ") and baseline corticosteroid use ("prednisone  $> 5$  mg/day" vs "prednisone  $\leq 5$  mg/day") and randomized 1:1 to receive either inebilizumab or placebo within each stratum. In the Japan population, no further stratification will be applied due to the small sample size, and subjects will be randomized 1:1 to receive either IV inebilizumab or placebo.

A subject is considered randomized into the study when the Investigator notifies the IXRS that the subject meets eligibility criteria and the IXRS provides the assignment of treatment group and allocates treatment, including IP kit number.

Additional details are provided in the IXRS Manual.

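### The double-positive rule in Protocol Section 6.2.3 cannot be applied to subjects whose only known prior positive is AChR, because they need not be tested for MuSK

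*Protocol*

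**What the plan says.** Protocol Section 6.2.3 contains three instructions that have to work together.

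- Prior positive result for AChR or MuSK: "that specific antibody will be tested in the screening labs to confirm positivity".
- No prior testing, or results not known: "both AChR and MuSK antibodies should be tested during screening".
- Placement: "If a subject is positive for both anti-AChR and anti-MuSK antibodies, the subject should be enrolled in the MuSK-Ab+ group".

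The section also makes central confirmation of at least one antibody a condition of randomisation: "If a subject is not confirmed to be positive for anti-AChR or anti-MuSK antibodies by the central laboratory, then the subject cannot be randomized". Table 2 lists the sample as "Serum for AChR or MuSK serostatus", and Inclusion Criterion 3a accepts either antibody. Under Section 6.1.1, a re-screened subject with a positive central result from the previous 6 months does not repeat the serostatus test.

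Placement has consequences. Section 7.3.2 states: "Subjects will be enrolled into either the AChR-Ab+ or MuSK-Ab+ population". Stratification and 1:1 randomisation then take place within that population. Section 6.1.2 adds: "The duration of the RCP will be 52 weeks for the AChR-Ab+ population and 26 weeks for the MuSK-Ab+ population". Antibody status is a covariate in the primary model (Section 9.4.1). Key secondary endpoints 2 to 5 are each defined within one of the two populations (Section 9.4.2), and all four are in the fixed testing sequence (Section 9.4.5). SAP Section 3.4.3.2 selects the subjects for these endpoints by baseline antibody status. Its visible text does not say whether that means the population assigned at randomisation or complete serology.

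**The concern.** The placement rule needs two test results, and one of the two testing routes asks for only one. If the known prior positive is AChR, nothing in the visible text requires a MuSK assay, so a co-existing MuSK antibody can go unseen and the subject is enrolled as AChR-Ab+. For double-positive subjects, the population then depends on whether a prior result was known.

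At stake is the definition of the populations. Sections 2.1 and 2.2 describe different antibody biology in the two diseases and a stronger response to CD20 depletion in MuSK-Ab+ disease, and the plan makes population-specific confirmatory claims. Under its own rule, the AChR-Ab+ population should contain no double-positive subjects. As the tests are ordered, it may contain some, and the MuSK-Ab+ population may lack subjects the rule would have placed there.

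**Working it through.** **Step 1. Follow each type of subject through Section 6.2.3.**

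| Subject | Assay required at screening | Group reached | Agrees with the rule? |
|---|---|---|---|
| AChR only, any history | AChR, or both | AChR-Ab+ | Yes |
| MuSK only, any history | MuSK, or both | MuSK-Ab+ | Yes |
| Double-positive, prior MuSK result | MuSK | MuSK-Ab+ | Yes |
| Double-positive, both known beforehand | Both, on a natural reading | MuSK-Ab+ | Yes |
| Double-positive, no known result | Both | MuSK-Ab+ | Yes |
| Double-positive, only AChR known | AChR | AChR-Ab+ | **No** |

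One row fails, and in one direction only. The gap can leave double-positives in AChR-Ab+; it puts nobody wrongly into MuSK-Ab+.

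**Step 2. Reproduce the plan's own figures.** Inputs from Protocol Section 9.2: 115 per arm overall, 94 per arm AChR-Ab+, 21 per arm MuSK-Ab+, difference 2, SD 4, two-sided alpha 0.05. Power comes from the noncentral t distribution with noncentrality 2 / (4 × √(2/n)).

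- Overall, n = 115: noncentrality 3.79, power 96.5% (plan: more than 95%).
- AChR-Ab+, n = 94: noncentrality 3.43, power 92.6% (plan: at least 90%).
- MuSK-Ab+, n = 21: smallest difference reaching p = 0.05 is t(0.975; 40) × 4 × √(2/21) = 2.49 (plan: 2.5).

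All three reproduce, and none is in dispute.

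**Step 3. Move the misplaced subjects.** Let f be the share of the 188 AChR-Ab+ subjects who would also test MuSK-positive. The documents give no value, so f is an assumption. Treating enrolment as fixed, 188 × f subjects move to MuSK-Ab+.

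| f (assumed) | Subjects moved | AChR-Ab+ power | MuSK-Ab+ detectable difference | Moved, as share of enlarged MuSK-Ab+ group |
|---|---|---|---|---|
| 0.5% | 0.9 | 92.5% | 2.47 | 2% |
| 1% | 1.9 | 92.4% | 2.44 | 4% |
| 2% | 3.8 | 92.2% | 2.38 | 8% |
| 5% | 9.4 | 91.4% | 2.24 | 18% |

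The last column is 188f / (42 + 188f); at 5%, 9.4 / 51.4 = 18%. The overall N of 230 and overall power do not change.

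**Step 4. Effect on the AChR-Ab+ estimate.** If the treatment effect in misplaced subjects differs from that in the remaining AChR-Ab+ subjects by D points, the AChR-Ab+ mean difference shifts by f × D. Taking D = 2 for illustration, as large as the planned effect itself, the shift is 0.005 × 2 = 0.01 to 0.05 × 2 = 0.10 MG-ADL points.

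**The case against.** The strongest reply is that this is a small wording gap in a defensible design. Confirming the known antibody is reasonable, the text says a double-positive subject should go to MuSK-Ab+ and does not forbid a second assay, and the laboratory and IXRS manuals may cover the point. It is true that the restriction to one assay is inferred from the contrast between the two testing sentences. But nothing visible requires the second assay, so a site that follows the protocol can place a subject against its own rule.

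It could also be said that defining the populations by the confirmed antibody would serve as well. That would remove the contradiction on paper. However, subjects without known results would still be tested for both, so a rule for double-positives would still be needed and identical subjects could still be split.

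A reader might infer more than the documents support:

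- *That the two populations are sorted by test history rather than serology.* They are not. Every randomised subject is centrally confirmed for an antibody, and five of the six routes in the table follow the rule.
- *That the treatment comparison or the primary result is biased.* Placement precedes 1:1 randomisation within population, so it is independent of arm, and the primary endpoint pools both populations.
- *That the different RCP lengths and infusion counts contaminate the confirmatory tests.* All of these tests are at Week 26. Up to then the assessments are common and the infusion days (1 and 15) are the same. The AChR-Ab+ Day 183 infusion follows that visit's assessments (Section 6.1.2 and Table 3, note i).
- *That the MuSK-Ab+ group falls short of 42.* That is a separate enrolment target; misplaced AChR-Ab+ subjects do not show a shortfall.
- *That misplaced subjects can never be identified.* Some row labels in the schedules are missing from the public text, so whether the second antibody is measured elsewhere cannot be determined.

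Finally, the protocol anticipates similar efficacy in both populations within 26 weeks (Sections 4.4 and 6.1.2). If so, D in Step 4 is near zero and the estimates hardly move. The label would still be inexact.

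**Conclusion.** The point stands for one subset: double-positive subjects whose only known prior positive is AChR. For them the plan states a placement rule and does not order the test needed to apply it.

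The effect is limited to the population in which they are randomised, their value of the antibody covariate, the RCP they follow, and the population labels in key secondary endpoints 2 to 5. It concerns what those populations are, not power or type I error. The size rests on an assumed rate of 0.5% to 5%, giving about 1 to 9 of 188 subjects. Even at the top of that range AChR-Ab+ power is 91.4%, above the planned 90%. The range takes every such subject to have been placed on AChR testing alone; any whose MuSK status was found by another route would lower the count. At the upper end the moved subjects would form 18% of the enlarged MuSK-Ab+ group, which matters for reading the results of so small a population.

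**What to change.** Amend Section 6.2.3 and the serostatus row of Table 2 so that the central laboratory runs both AChR and MuSK serostatus on the screening serum of every subject, with both results available before the population is entered in the IXRS. Apply the same requirement to re-screened subjects whose stored result covers one antibody only. The placement rule can then be followed for everyone.

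For subjects already randomised, keep the randomised population for the main analysis and say so in SAP Section 3.4.3.2. Where stored serum and consent allow, run the missing assay and add a sensitivity analysis of key secondary endpoints 2 to 5 by full serology.

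The cost is one additional assay per subject with a prior positive result, plus wording changes in the protocol and probably the laboratory manual. The plan already runs both assays for subjects without known results, and serum for serostatus is already collected at screening, so no extra visit or subject is implied; the documents do not give sample volumes. The retrospective part is optional, because storage and consent for leftover samples vary by country.
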